7.6.2.5 Deaths

All deaths recorded on the status page, the AE page, or SAE page (with a death date, or cause of death, or outcome or SAE categorization present) of the CRF will be reported. Any deaths that occur during the study will be described in depth as narrative in the CSR. All Adverse events with the outcome of death reported during the study will be listed.

7.6.2.6 Other Serious Adverse Events

SAEs are captured on a special CRF page. Summaries of all SAEs, related SAEs, and SAEs leading to discontinuation will be provided for 2 periods (Double-Blind Treatment Period, Cumulative Abatacept Period). All SAEs will be listed.

7.6.2.7 Adverse Events Leading to Discontinuation of Study Therapy

AEs leading to discontinuation of study drug are identified as those AEs with an action code of 5 on the CRF page (5 = discontinued study drug). All such AEs will be summarized for the Double-Blind Treatment Period and cumulative abatacept period. All AEs leading to discontinuation will be listed.

7.6.2.8 Multiple Adverse Events

Several descriptive summaries of adverse events that takes into account the number of occurrences that an AE was reported by individual patients will be provided. In order to prepare these summaries, the CRF data will be processed according to standard BMS algorithms to categorize each line of patient data as a new occurrence or a continuation of an existing event. This determination will be based upon onset and resolution dates. Each line of patient data will represent the maximum severity observed as well as the last known assessed relationship to study medication by the investigator.

This data will be presented as the rate per 100 years of patient exposure. Exposure to study medication will be calculated according to approved standard BMS algorithms as well.

As an example, if 5 patients report 7 unique episodes of headache and had a combined cumulative exposure of 20 years to study medication, the incidence rate is reported as $7 / 20 * (100)$ or 35 cases per 100 patient years of exposure.

The following summary tables will be provided:

- A table showing the total number and rate (exposure adjusted) of occurrences for all AEs occurring in at least 5% of the subjects treated will be presented for the double-blind treatment period and the cumulative abatacept period separately.
- For all AEs as well as for AEs of special interest:
 - A table showing total number of events and rate (exposure adjusted) will be presented for the Double-Blind Treatment Period (overall) and the cumulative abatacept period (by 6 months time intervals) separately.
 - A table showing the number of subjects experiencing an AE once or multiple times will be presented for the Double-Blind Treatment Period and the cumulative abatacept period separately.

- Listing displaying the unique instances of all AEs, i.e., after duplicates have been eliminated and overlapping and contiguous occurrences of the same event have been collapses.

No formal comparisons are made between treatments. No formal statistical testing will be performed, only summary statistics are provided.

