7.4 Extent of Exposure

7.4.1 Study Therapy

The extent of exposure during the double-blind (for the As-treated Analysis Population) and the cumulative abatacept periods (for the cumulative abatacept population) will be summarized in the following ways:

- Number of abatacept/placebo injections
- Number of days a subject is known to be on study drug.

The number of injections subjects received will be based on the study medication page of the CRF when it is indicated that a subject received the study medication.

The number of days the subject is known to be on study drug (exposure to study drug) during the Double-Blind Period is calculated as:

For subjects who discontinued during the Double-Blind Period OR completed the Double-Blind Period but not treated in open-label period OR not treated in the open-label period within 56 days of the last injection in the Double-Blind Period:

Exposure in days = (date of last injection in the Double-Blind Period - date of first injection in the Double-Blind Period + 1) + 56.

For subjects who were treated in the open-label within 56 days of the last injection of the Double-Blind Period:

Exposure in days = (date of first injection in the open-label period - date of first injection in the Double-Blind Period).

Exposure in cumulative abatacept period for subjects who discontinued treatment in double-blind or open-label OR who completed double-blind and not treated in Open-label or who completed open-label is calculated as:

Exposure in days = (date of last abatacept injection - date of first abatacept injection + 1) + 56

In case a patient randomized to abatacept does not go into open-label within 56 days post last dose in double-blind, the exposure has to be adjusted for the gap exceeding 56 days.

Exposure in cumulative abatacept period for subjects who are on-going in open-label period is calculated as:

Exposure in days = cut-off date - date of first abatacept injection with cut-off date = the date database lock date.

For subjects randomized to placebo, the date of first abatacept injection is date of first open-label abatacept treatment. For subjects randomized to abatacept, the date of first abatacept injection is the date of first double-blind abatacept treatment.

The date of last abatacept injection can be the last date of abatacept in double-blind if the subject is not treated in open-label or the date of last abatacept injection in open-label if subject is treated in open-label.

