The offset of 56 days is the length of 2 regular dosing cycles and represents approximately 4 times the half-life of abatacept in humans.

Summaries of exposure to study drug during the Double-Blind Period and the cumulative abatacept period will show the distribution of the number of injections and days on drug, together with the means, standard deviations, medians, minimum and maximum. For the Double-Blind Period the presentation will be by treatment group and for the cumulative abatacept period all subjects will be presented together.

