7.6.2 Adverse Events of Interest

The following adverse events of special interest will be summarized by PT and treatment groups during the Double-Blind Treatment and cumulative abatacept periods. A subject listing will also be provided.

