7.6.2.4 Injection Reactions

- 1) Systemic Injection Reactions are defined as pre-specified systemic AEs (such as hypersensitivity reactions) occurring during the first 24 hours after SC injection.
- 2) Local Injection Site Reactions (LISR) are defined as those AEs that occur at the site of SC injection. A pre-specified list of MedDRA codes for Local Injection Site Reaction (LISR) events of interest will be used to identify the local injection site reactions.

The frequency of pre-specified systemic injections (1) and local injection site reactions (2) (defined using a BMS custom SMQ) occurring during each study period (Double-Blind Treatment Period, Cumulative Abatacept Period) will be provided for (1) and (2) separately and for each study period separately. These AEs will also be summarized by intensity and a listing of all these reported AEs will be provided

In addition to the summary of LISR, the following 5 AEs PTs will be summarized separately for the each study period (Double-Blind Treatment Period or Cumulative Abatacept Period): *Injection Site Erythema, Injection Site Pain, Injection Site Pruritus, Injection Site Haematoma, and Injection Site Swelling.*

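### SAP 7.6.2.8 states no denominator for injection-reaction rates; the SAP's only exposure formula would dilute them with 56 injection-free days and make late intervals fall

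*SAP*

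**What the plan says.** SAP 7.6.2.8 tabulates event counts and rates per 100 patient-years "For all AEs as well as for AEs of special interest". The double-blind period is shown overall and the cumulative abatacept period by 6-month intervals. For the exposure behind these rates it points to approved standard company algorithms and does not cite SAP 7.4.1.

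SAP 7.6.2 opens its list with "The following adverse events of special interest will be summarized by PT and treatment groups", and injection reactions (7.6.2.4) are on that list. Systemic reactions are pre-specified events "occurring during the first 24 hours after SC injection". For local reactions the wording is "Local Injection Site Reactions (LISR) are defined as those AEs that occur at the site of SC injection", with a code list but no time limit.

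SAP 7.4.1 is the only place where exposure is written out:

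- Cumulative abatacept period, subjects who stopped or completed: "Exposure in days = (date of last abatacept injection - date of first abatacept injection + 1) + 56".
- Cumulative abatacept period, subjects still in open label: "Exposure in days = cut-off date - date of first abatacept injection with cut-off date = the date database lock date". There is no tail.
- Double-blind period, subjects who start open label within 56 days of their last double-blind injection: "Exposure in days = (date of first injection in the open-label period - date of first injection in the Double-Blind Period". Again there is no tail. Everyone else gets the extra 56 days.

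The tail is justified by drug persistence: "The offset of 56 days is the length of 2 regular dosing cycles and represents approximately 4 times the half-life of abatacept in humans". SAP 7.6.1 counts adverse events over the same 56 days, and the cumulative abatacept population is reported as one combined group.

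**The concern.** A tail of about four half-lives suits events that residual drug may cause. An injection reaction is triggered by the injection, and no injections are given in the tail. If the tail sits in the denominator, the rate per patient-year of a risk specific to the subcutaneous route is diluted.

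The dilution is not even over time. It falls almost entirely in the later 6-month intervals, because that is where subjects finish. The by-interval table exists to show change over time, so a reader could conclude that injection reactions fade with continued treatment when the denominator alone produced the fall.

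**Working it through.** **The plan's own figures.** The worked example in 7.6.2.8 reproduces: 7 / 20 x 100 = 35 per 100 patient-years. The 56-day offset also reproduces: Protocol 3.3.1 equates 5 half-lives with 70 days, so one half-life is 70 / 5 = 14 days, and 4 x 14 = 56.

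**Inputs.** Abatacept runs from Day 1 (abatacept arm) or Day 169 (placebo arm) to Day 357 (SAP 2.1). Allocation is 1:1. Subjects are assumed to complete on schedule. Let c be the days after the last injection still credited as at risk. It is not in the documents, so it is varied over 0, 1 and 7.

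**Overall rate, completers, Year 1 data.** Counted days = (last - first + 1) + 56. Shortfall = (56 - c) / counted days.

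| | Counted days | c = 0 | c = 1 | c = 7 |
|---|---|---|---|---|
| Abatacept arm | 357 + 56 = 413 | 56/413 = 13.6% | 55/413 = 13.3% | 49/413 = 11.9% |
| Placebo arm, on open-label abatacept | 189 + 56 = 245 | 56/245 = 22.9% | 55/245 = 22.4% | 49/245 = 20.0% |
| Pooled, as reported | 658 | 112/658 = 17.0% | 110/658 = 16.7% | 98/658 = 14.9% |

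With 0-30% dropout (assumed; half in each period, timing uniform), the pooled shortfall runs from about 15% to 19%.

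**By 6-month interval.** Intervals of 182 days are assumed; the SAP gives no cut-points. The table takes one completer from each arm and counts days from first abatacept.

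| Interval | Counted days | At risk, c = 0 | c = 1 | c = 7 |
|---|---|---|---|---|
| 1 | 182 + 182 = 364 | 364 | 364 | 364 |
| 2 | 182 + 63 = 245 | 175 + 7 = 182 | 176 + 8 = 184 | 182 + 14 = 196 |
| 3 | 49 + 0 = 49 | 0 | 0 | 0 |

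In interval 2 a constant true rate would appear at 182/245 = 74%, 184/245 = 75% or 196/245 = 80% of its value, that is 20-26% low. In interval 3 the apparent rate is zero apart from late local reactions. With 180- or 183-day intervals, interval 2 is again at 74-80% and interval 3 at 0-8% (the 8% being 4 of 53 days, for 180-day intervals and c = 7).

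**Double-blind table.** A subject who enters open label on schedule counts 169 - 1 = 168 days with no tail. Assume 10% stop and do not enter, with last doses spread evenly over the 24 weekly doses (mean Day 81.5), and take c = 7. Tail days per subject randomised are 0.10 x 49 = 4.9. Counted days are 0.10 x (81.5 + 56) + 0.90 x 168 = 13.75 + 151.2 = 164.95. The shortfall is 4.9 / 164.95 = 3.0%. The same sum gives about 1.5% if 5% stop and 6% if 20% stop.

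**The case against.** The strongest objection is that the denominator is not known. A reader might take it as established that these rates divide by exposure including the 56 days. The documents do not say so: 7.6.2.8 defers to company algorithms outside the documents, and 7.4.1 defines exposure for the exposure summary. Applying 7.4.1 is a reasonable inference, since it covers the same two periods and matches the event window, but it remains an inference. This part stands, and it is itself a reason to state the denominator.

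A reader might also infer that no injection reaction can arise in the tail. That is true by definition only for systemic reactions. A late local reaction is not excluded by 7.6.2.4 and would be counted.

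A third tempting reading is that published rates would be 12-20% low. Those are the two arms' separate figures with 7 days credited. The cumulative table pools the arms, so neither would be reported.

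It can further be said that a rate per year of defined exposure is internally consistent, because events and exposure share one window. That is fair. The rate is low only as a measure of reactions while injections are being given. Dosing time is an imperfect standard too: with weekly dosing, the 24-hour systemic window covers about one day in seven (14%). This favours a rate per injection over a rate per patient-year of dosing.

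Finally, the tables are descriptive. Injection reactions also appear in 7.6.2.4 as frequencies, by intensity and in listings, which this denominator does not touch. That limits the importance of the point but does not correct the by-interval display.

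**Conclusion.** The point holds conditionally. SAP 7.6.2.8 does not define its exposure. If the 7.4.1 formula is used, completers' pooled cumulative abatacept rate of injection reactions in the Year 1 report is about 15-17% low. A constant rate would appear about 20-26% low in the second 6-month interval and near zero in any interval beyond 12 months. These figures assume completion on schedule, equal arms, 0 to 7 days credited after the last injection, and 182-day intervals for the by-interval result.

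The effect is smaller at the Month 6 report, where subjects still in open label carry no tail. In the double-blind table it is likely small: about 3% if 10% do not enter open label, an assumed figure. A reader might infer a material bias in the comparison with placebo. The documents do not support that, since only the difference between arms in the share with a tail would matter. No test, endpoint or hypothesis is affected. What needs correcting is the risk of misreading the by-interval table.

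**What to change.** In SAP 7.6.2.8, write out the exposure definition or cite 7.4.1. For the injection reactions of 7.6.2.4, report events per 100 injections, overall and by interval, using the injection count already derived in 7.4.1. Keep the 56-day exposure for all other adverse events.

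The cost is a sentence or two in the SAP and one extra denominator. The by-interval version also needs the injections allotted to intervals by date. No new data are collected and no other result changes. The drawback is that injection-reaction rates would be on a different scale from the other adverse events and from programme-standard tables. The standard rate per 100 patient-years can therefore be kept alongside, with a footnote that its denominator includes time after the last injection.

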7.6.3 Laboratory Evaluation

Unless otherwise specified, laboratory data obtained after the start of study medication dosing up to the first dose in the open-label period or up to and including 56 days after the last double-blind dosing date, whichever occurs first will be considered as obtained during Double-Blind Treatment Period. For the cumulative abatacept period, laboratory data obtained after the start of abatacept up to and including 56 days after the last abatacept dose will be considered as obtained during the cumulative abatacept period.

7.6.3.1 Marked Laboratory Abnormalities

Laboratory abnormalities will be reported for the same periods as for the AEs, i.e., Double-Blind Treatment Period and Cumulative Abatacept Period. Laboratory measurements will be included in the analysis for the Double-Blind Treatment Period if the measurement date is on or after the first day of dosing and up to first dose in the open-label period or 56 days post the last dosing day in the Double-Blind Treatment Period whichever is earlier. Laboratory measurements will be included in the analysis for the Cumulative Abatacept Period if the measurement date is after first abatacept dose date up to the 56 days post last abatacept dose date.

Laboratory abnormalities are identified using a pre-defined set of marked abnormality criteria. The criteria will be listed in the study report.

The frequency of subjects with any marked laboratory abnormality will be presented by laboratory test during the Double-Blind Treatment Period and separately, during the cumulative abatacept period. The results are based on the As-treated analysis population for the double-blind period and based on the cumulative abatacept population for the cumulative abatacept period.

The pre-specified criteria used for classifying laboratory test results as markedly abnormal will be listed.

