5.3 Safety Assessments

On Day 1, the results of all assessments must be reviewed to ensure that eligibility requirements are met before contacting the Central Randomization System for the subject's randomization assignment.

Subjects who terminate treatment early should complete the appropriate Early Termination Visit and the Post Drug Follow-up Visits. The Early Termination Visit should be as soon as possible after the last dose of study medication.

All assessments should be performed or administered prior to study drug administration unless otherwise indicated.

Only data for the procedures and assessments specified in this protocol should be submitted to BMS on a case report form. Additional procedures and assessments may be performed as part of standard of care; however, data for these assessments should remain in the subject's medical record and should not be provided to BMS, unless specifically requested from BMS.

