6 STUDY PERIODS, TREATMENT REGIMENS AND POPULATIONS FOR ANALYSES

6.1 Study Periods

In this study, there are five study periods: Screening period, Double-Blind Period, Open-Label Period, Cumulative Abatacept Period and Follow-up Period. The following analysis periods defined below are for analysis purposes. The definitions below indicate the data to be included in the analysis of each specified period.

- **Screening period:** It covers the time period which starts from the day of enrollment and lasts until the initiation of the randomized Double-Blind Period.
- **Double-Blind Treatment Period:** It starts at the time of the first dose of blinded treatment and continues up to 56 days post last dose in the Double-Blind Period or prior to the first dose in the open-label period, whichever is earlier for safety (AE and laboratory summaries). Up to 42 days post last dose in the Double-Blind Period or prior to the first dose in the open-label period, whichever is earlier for efficacy analyses. Up to 21 days post last dose in the Double-Blind Period or prior to the first dose in the open-label period, whichever is earlier for on-treatment immunogenicity summaries.
- **Open-Label period:** It starts at the time of the first dose of open-label treatment and continues up to 56 days post last dose for safety (AE and laboratory summaries). Up to 42 days post last dose for efficacy analyses and up to 21 days post last dose for the on-treatment immunogenicity summaries.
- **Cumulative Abatacept Period:** It starts at the time of the first dose of abatacept (either in the Double-Blind Period for the subjects randomized to abatacept or in the open-label period for the subjects randomized to placebo) and continues up to 56 days post last dose of abatacept for safety (AE and laboratory summaries) and up to 21 days post last abatacept dose for the on-treatment immunogenicity summaries. The last abatacept dose can be last dose in Double-Blind Period for subjects not treated in the open-label period.
- **Follow-up Period:** immunogenicity summaries are provided for the follow-up period that starts at Day 22 post last dose and continues up to last assessment of immunogenicity in the study.

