7.6 Safety

The safety analysis endpoints described in this section are considered as secondary endpoints. For their analysis, there will be no statistical testing of group differences.

Analysis of all safety data will follow the BMS standard safety data conventions³ and abatacept program safety conventions⁴.

All summaries of safety parameters during the Double-Blind Treatment Period will be provided by treatment groups. All safety assessments will be included in the summary tables if the onset date is on or after the first dose date and up to 56 days post the last dosing day in the Double-Blind Treatment Period or the first dosing date in the open-label period, whichever occurs first. Presentations for the Double-Blind Treatment Period will be provided by “as treated” treatment group for the as-treated analysis population, unless otherwise specified.

These safety endpoints will also be summarized during the cumulative abatacept period (from the first day of abatacept treatment in the study up to 56 days after the last abatacept treatment in the study) for the cumulative abatacept population. For the cumulative abatacept population all subjects will be combined in one group.

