8.2 Baseline Measures

For each subject, the baseline value of a parameter is defined as the last assessment of that parameter on or prior to the date/time of the first dose of the double-blind study medication.

If time of measurement of a parameter or time of first dose are missing, then the baseline value is defined as the last assessment of that parameter on or prior to the date of the first dose of the double-blind study medication.

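### The laboratory inclusion rule for the double-blind marked-abnormality table, read literally, takes in the pre-dose Day 1 baseline sample and conflicts with other SAP sections

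*SAP*

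**What the plan says.** SAP 7.6.3.1 has two sentences on which results count. For the double-blind table a measurement is included "if the measurement date is on or after the first day of dosing and up to first dose in the open-label period" or until 56 days after the last double-blind dose, whichever is earlier. For the cumulative abatacept table it is included "if the measurement date is after first abatacept dose date up to the 56 days post last abatacept dose date".

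Four other SAP sections bear on the same sample:

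- 6.1, defining the Double-Blind Treatment Period: "It starts at the time of the first dose of blinded treatment".
- 7.6, the general safety rule: "All safety assessments will be included in the summary tables if the onset date is on or after the first dose date".
- 7.6.3, the general laboratory rule: "laboratory data obtained after the start of study medication dosing up to the first dose in the open-label period". It opens with "Unless otherwise specified".
- 8.2, the baseline value: "the last assessment of that parameter on or prior to the date/time of the first dose of the double-blind study medication".

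On the order of events, Protocol 5.3 says: "All assessments should be performed or administered prior to study drug administration unless otherwise indicated". Protocol 3.1.2 and 4.5 repeat this for office visits and name blood draws. The order in Protocol 5.1.2 lists blood draws just before study drug.

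**The concern.** A Day 1 sample taken as planned precedes any exposure. An abnormality in it cannot be a treatment-period finding, yet its date meets the double-blind test in 7.6.3.1. The general rule in 7.6.3 would exclude it, but that rule gives way where another section specifies otherwise, and 7.6.3.1 does. A programmer who follows the most specific section would count the sample. One who follows the period definition in 6.1 would not.

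The proportion of subjects with marked laboratory abnormalities is a named secondary safety endpoint (Protocol 8.3.2). Protocol 3.3.2 admits subjects with hemoglobin down to 8.5 g/dL, white cells down to 2,500/mm³, lymphocytes down to 500/mm³ and platelets down to 50,000/mm³. Some pre-dose values could therefore be abnormal enough to count. Both arms' rates could rise for reasons unrelated to treatment, and the ratio between them would move toward 1.

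**Working it through.** **1. Is the Day 1 sample counted?** Take a subject randomized to abatacept whose Day 1 blood is drawn before the injection.

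| SAP section | Start of the window | Pre-dose Day 1 sample |
|---|---|---|
| 6.1 | time of first dose | excluded |
| 7.6 | date of first dose, inclusive | included |
| 7.6.3 | after dosing starts | excluded |
| 7.6.3.1, double-blind | first dosing day, inclusive | included |
| 7.6.3.1, cumulative | after the first abatacept dose date | excluded |
| 8.2 | at or before first dose | is the baseline |

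No section removes the baseline record from the 7.6.3.1 double-blind table. Within that one section, the same sample counts in the double-blind table and not in the cumulative table, although for this subject the cumulative period starts at the same dose.

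**2. How large could the effect be?** The plan gives no figure to reproduce, so every rate here is an assumption. Let b be the share of subjects who meet a criterion pre-dose, r the rate of new abnormality among the rest, and q the share of pre-dose abnormal subjects who meet the criterion again later in the period. Take b and q as equal in the two arms.

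- Current rule: b + (1 − b)r
- Post-dose rule: bq + (1 − b)r

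With b = 10%, r = 3% on placebo and r = 8% on abatacept, the current rule gives 0.10 + 0.90 × 0.03 = 12.7% and 0.10 + 0.90 × 0.08 = 17.2%, a ratio of 1.35. The post-dose rule gives:

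| q | Placebo | Abatacept | Ratio |
|---|---|---|---|
| 0 | 2.7% | 7.2% | 2.67 |
| 0.5 | 7.7% | 12.2% | 1.58 |
| 0.8 | 10.7% | 15.2% | 1.42 |
| 1 | 12.7% | 17.2% | 1.35 |

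The absolute difference is (1 − b)(0.08 − 0.03) = 0.90 × 0.05 = 4.5 points under both rules, whatever q is. If q differs between arms, the post-dose difference changes by b(q on abatacept − q on placebo). For example, if pre-dose abnormal subjects later meet the criterion at the same 3% and 8% as everyone else, it becomes 4.5 + 0.10 × 5 = 5.0 points.

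**3. Other prevalences under the current rule, same new rates.**

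- b = 5%: 0.05 + 0.95 × 0.03 = 7.85% and 0.05 + 0.95 × 0.08 = 12.6%, ratio 1.61.
- b = 20%: 0.20 + 0.80 × 0.03 = 22.4% and 0.20 + 0.80 × 0.08 = 26.4%, ratio 1.18.

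**4. How many subjects?** With 86 per arm (SAP 5), the subjects counted on the pre-dose sample who have no later persistence number 86 × b × (1 − q), before allowing for chance. At b = 10% that is 8.6 if q = 0, 4.3 if q = 0.5 and none if q = 1. The chance that an arm contains at least one pre-dose abnormal subject is 1 − (1 − b)^86, which is 58% at b = 1% and 93% at b = 3%.

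**The case against.** The strongest answer is that the SAP already excludes the sample. Section 7.6.3.1 reports by the Double-Blind Treatment Period, and 6.1 defines that period, for laboratory summaries by name, from the time of the first dose. Section 7.6.3 and the cumulative-period sentence agree. This stands in part: a reader might infer that the baseline sample will certainly be reported as an on-treatment abnormality, and the documents do not support that. They do leave two inclusive rules, in 7.6 and 7.6.3.1, set against three exclusive ones, with the most specific rule on the inclusive side.

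A second answer concerns size. A reader might infer that the rule hides a real treatment difference and that the fix would restore a ratio of 2.67. That figure needs every pre-dose abnormality to have cleared at all later visits. A persistent abnormality still counts after the fix, because 7.6.3.1 states no baseline adjustment, and the absolute difference barely moves.

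Third, the marked-abnormality criteria are not reproduced in the SAP, and the sponsor's safety conventions (SAP 7.6 and 8.7) are only referenced. Either might account for baseline. Nor do the documents show that values near the eligibility limits would meet a marked criterion.

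Finally, safety results are not tested, efficacy is untouched, and randomization makes baseline abnormality equal between arms in expectation. All of this is correct, and it limits the importance of the point. It does not settle which rule should be programmed.

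**Conclusion.** The concern holds as an internal conflict in the SAP. Read literally, 7.6.3.1 and 7.6 admit the pre-dose Day 1 sample as a double-blind result. SAP 6.1, 7.6.3 and the cumulative-period sentence exclude it, and 8.2 calls it baseline.

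The consequence is limited to descriptive safety tables. Rates in both arms could be raised by subjects who are abnormal only before dosing. That dilutes the ratio but leaves the absolute difference nearly unchanged, provided persistence is similar in the two arms. The actual size cannot be determined. The illustration depends on assumed prevalence, new rates and persistence, and the gain from the fix runs from nothing (all persist) to a ratio of 2.67 in place of 1.35 (none persist).

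The finding also assumes that hematology and chemistry are sampled on Day 1. Those rows of Protocol Table 5.1-2 are not in the text available for review, but the Day 1 hsCRP entry and the Day 1 laboratory window in SAP Table 8.5-1 support it.

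**What to change.** In SAP 7.6.3.1, and for laboratory data in 7.6, include a measurement in the double-blind tables only if its date and time fall after the first double-blind injection, and exclude the record that Section 8.2 selects as baseline. Treat a Day 1 sample with no recorded time as pre-dose, which matches the missing-time rule in 8.2. Word the cumulative abatacept rule in parallel, counted from the first abatacept injection. This brings 7.6 and 7.6.3.1 into line with 6.1 and 7.6.3.

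The cost is a sentence in each of the two sections and one programming filter. No data collection changes. Abnormalities that persist from baseline will still be counted unless the criteria themselves adjust for baseline.
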